4.1.3 Criteria for Starting Subsequent Cycles

A cycle may be repeated every 28 days, up to a maximum of 26 cycles. Larotrectinib will be administered continuously without breaks unless the patient meets criteria for holding or discontinuing larotrectinib as defined in [Section 5.1](#). Patients who experience progressive disease at any time on protocol therapy will be taken off therapy. Patients with solid tumors (Cohorts A & B) who do not have progressive disease will follow the guidelines outlined in [Section 4.1.3.1](#), [Section 4.1.3.2](#) and [Section 4.1.3.3](#).

4.1.3.1 Patients with Localized Disease who Achieve Stable Disease or a Partial Response that Renders Disease Resectable:

Patients with localized disease who achieve sufficient tumor shrinkage to have disease resection (for whom a complete resection is anticipated to be likely without functional, neurologic, or significant cosmetic deficit) will undergo surgical resection of their residual tumor after a minimum of 6 cycles of therapy (see [Section 13.1](#) for surgical guidelines). Such patients may receive up to 1 additional cycle of therapy after their tumor is deemed resectable during surgical planning. Larotrectinib will be held for 24 hours prior to surgery. Following surgery, patients with IFS or CMN who achieve a gross total resection and all other patients with solid tumors who achieve a resection with negative margins ([Section 13.2](#)) will have completed planned therapy and enter Follow-up ([Section 7.2](#)). Patients who have an incomplete resection or positive margins for diagnoses other than IFS/CMN will resume protocol therapy following surgery. Therapy may be resumed as soon as 24 hours post-operatively once it has been determined that the patient meets protocol criteria to resume therapy and the patient is tolerating enteral fluids.

4.1.3.2 Patients who Achieve Stable Disease or a Partial Response and Do Not Have Localized, Resectable Disease:

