4.3.2 Required Observations for Cycles 2+, Cohorts A & B

- a. Hx/Wt /Ht/BSA. Within 7 days prior to subsequent cycles and at the end of study treatment.
- b. Performance status. Prior to subsequent cycles.
- c. Physical exam (including VS and neurologic examination). Prior to subsequent cycles and at the end of study treatment.
- d. CBC/diff/platelets: Prior to subsequent cycles. If patients have Grade 4 neutropenia then CBCs should be checked every 3 to 4 days until recovery to Grade 3 or until meeting the criteria for dose limiting toxicity.
- e. Electrolytes including Ca⁺⁺. Prior to subsequent cycles.
- f. Creatinine, ALT, bilirubin. Prior to subsequent cycles.
- g. Disease evaluation. After cycles 2, 4, 6, 9, 12, 16, 20, and 24. If the institutional investigator determines that the patient has progressed based on clinical or laboratory evidence, he/she may opt not to confirm this finding radiographically. Please refer to [Section 10.4](#) for Confirmation of objective response by RECIST 1.1.
- h. Bone marrow evaluation. With Disease evaluation. Bone marrow aspirate and/or biopsy should only be performed on patients with solid tumors with bone marrow involvement at baseline. If the institutional investigator has determined the patient has progressed based on clinical or laboratory evidence, he/she may opt not to confirm this finding on marrow pathology.
- i. Circulating tumor DNA. On Day 1 of Cycle 2, at the end of cycle 6 (Day 1 of Cycle 7 or prior to local control), and at the time of progression. See [Section 7.3.2](#) for details.
- j. Tumor tissue submission. Submission of tumor tissue from any surgical resection or bone marrow evaluation for patients with involvement by tumor while on study is required. For patients who undergo resection of their tumor while on study, operative reports and hospital discharge summaries must be uploaded into RAVE following surgical resection. Submission of tumor tissue from any biopsy after progression is optional. See [Section 7.3.1](#) for details.
- k. Patient diary. Uploaded into RAVE at the end of each cycle. See [Appendix VII-A](#) and [Appendix VII-B](#) for details.
- l. Pregnancy test. Prior to subsequent cycles. Sexually active patients must use an acceptable method of birth control.

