9.3 Methods of Analysis

Response criteria are described in [Section 10.2](#). A responder is defined as a patient who achieves a best response (as defined in [Section 10.3.4](#)) of PR or CR on the study. Response rates will be calculated as the percent of evaluable patients who are responders, and confidence intervals will be constructed accounting for the two-stage design.

Toxicity tables will be constructed to summarize the observed incidence by type of toxicity and grade. A patient will be counted only once for a given toxicity for the worst grade of that toxicity reported for that patient. Toxicity information recorded will include the type, severity, time of onset, time of resolution, and the attribution(s) to the study regimen.

Time-to-event analyses (time to progression, progression-free survival, overall survival, and duration of response) will be computed one year after the last enrollment in a stratum. Duration of response will be defined among patients with a confirmed best response of either PR and CR, and will be defined as the time from the first observation of either PR or CR until either the first observation of PD (event) or last known observation of the patient (censored observation).

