9.4 Evaluability for Response

Any patient who is enrolled and receives at least one dose of larotrectinib will be considered evaluable for response provided: (1) the patient demonstrates progressive disease or death while on protocol therapy; or (2) the patient is observed on protocol therapy for at least one cycle and the tumor is not removed surgically prior to the time complete response or partial response is confirmed, or (3) the patient demonstrates a complete or partial response as confirmed according to protocol criteria. Patients who demonstrate a complete or partial response confirmed by central review will be considered to have experienced a response for the application of the rule given in [Section 9.2](#). All other patients will be considered non-responders. The evaluation period for determination of the best response will be 6 treatment cycles. All patients considered to have a response (CR or PR) must have imaging studies reviewed centrally at the COG. Centers will be notified by the COG about requests for scans of patients with stable disease. See [Section 7.4](#) regarding shipping instructions. Preliminary assessment of activity using institutionally provided tumor measurements will be entered into CDUS quarterly. The central review by COG will be provided as the final reviewed assessment of response when such becomes available.

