10.4 Best Response (Solid Tumors)

Two objective status determinations of disease status, by CT or MRI, obtained on two consecutive determinations, separated by at least a 3 week time period, are required to determine the patient's overall best response. Two objective status determinations of CR before progression are required for best response of CR. Two determinations of PR or better before progression, but not qualifying for a CR, are required for a best response of PR. Two determinations of stable/no response or better before progression, but not qualifying as CR or PR, are required for a best response of stable/no response; if the first objective status is unknown, only one such determination is required. Patients with an objective status of progression on or before the second evaluations (the first evaluation is the first radiographic evaluation after treatment has been administered) will have a best response of progressive disease. Best response is unknown if the patient does not qualify for a best response of progressive disease and if all objective statuses after the first determination and before progression are unknown.

Table 1: Sequences of objective statuses with corresponding best response.

| 1 st Status | 2 nd Status | 3 rd Status | Best Response |
|------------------------|------------------------|------------------------|---------------------|
| Progression | | | Progressive disease |
| Stable, PR, CR | Progression | | Progressive disease |
| Unknown | Progression | | Progressive disease |
| Stable | Stable | Progression | Stable |
| Stable, Unknown | PR, CR | Progression | Stable |
| Stable, Unknown | Unknown | Progression | Unknown |
| PR | PR | Progression | PR |
| PR | CR | Progression | PR |
| PR, CR | Unknown | Progression | Unknown |
| CR | CR | Progression | CR |
| Unknown | Stable | Progression | Stable |

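### Section 9.4, as worded, makes a patient with stable disease through the 6-cycle window who is then resected as planned not evaluable, although other sentences in the same section point to non-responder

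*Combined protocol and SAP*

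**What the plan says.** Section 9.4 gives a patient who has had at least one dose three alternative routes to being evaluable for response:

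1. progression or death on protocol therapy;
2. at least one cycle of observation on therapy, provided that "the tumor is not removed surgically prior to the time complete response or partial response is confirmed";
3. a confirmed complete response (CR) or partial response (PR).

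The same section then counts centrally confirmed CR/PR as response and adds "All other patients will be considered non-responders". It also says "The evaluation period for determination of the best response will be 6 treatment cycles".

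Section 9.3 sets the denominator: "Response rates will be calculated as the percent of evaluable patients who are responders". Section 9.1 says that Cohort A patients who do not meet the evaluability definition are replaced, and it allows 10% for this.

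Surgery is part of the plan. Section 4.1.3.1 is headed "Patients with Localized Disease who Achieve Stable Disease or a Partial Response that Renders Disease Resectable" and places resection after at least 6 cycles. Such patients "may receive up to 1 additional cycle of therapy after their tumor is deemed resectable during surgical planning". Section 4.3.2 schedules disease evaluation "After cycles 2, 4, 6, 9, 12, 16, 20, and 24". Section 10.4 requires the two determinations of status to be "obtained on two consecutive determinations, separated by at least a 3 week time period".

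**The concern.** Clause (2) is tied to the moment a response is confirmed, not to the end of the 6-cycle window. A patient whose disease stays stable never reaches that moment. If the tumor becomes resectable and is removed on schedule, the clause fails, although the patient completed the whole evaluation period and, under 10.4, already has a best response of stable.

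On that wording, entry to the primary denominator depends on outcome. Of two patients resected after Cycle 6, the one with a confirmed response stays in and the one with SD leaves and is replaced. In a cohort of 21, each such patient moves the reported ORR by several percentage points, always upward when the patient dropped is a non-responder.

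**Working it through.** **Step 1: the three routes, for SD at Cycles 2, 4 and 6 followed by planned resection.**

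- Route 1: no progression or death. Not met.
- Route 2: more than one cycle observed, but the tumor is removed with no CR/PR confirmed. Not met as worded.
- Route 3: no confirmed CR/PR. Not met.

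The literal result is not evaluable. The non-responder sentence and the 6-cycle period in 9.4 give the opposite result.

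**Step 2: reproduce the design.** Inputs from 9.2: continue with at least 6 responses in 9; declare effective with at least 16 in 21; null rate 0.60, alternative 0.85. The chance of success at response rate p is

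sum over x = 6 to 9 of P[Bin(9, p) = x] × P[Bin(12, p) ≥ 16 − x].

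At p = 0.60 the four terms are 0.0209 + 0.0363 + 0.0265 + 0.0067 = 0.0905 (plan: 9.05%), with early stopping 0.5174 (plan: 51.74%). At p = 0.85 the result is 0.9040 (plan: 90.40%). The stated figures are correct for the rate among evaluable patients.

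**Step 3: effect of dropping non-responders.** Let d be the share of all treated patients who are non-responders, dropped and replaced. With an all-treated rate p, the rate among those analysed is p/(1 − d). The documents give no value for d, so these are assumptions. At p = 0.60:

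| d (assumed) | Share of non-responders, d/0.40 | Dropped per 21 evaluable, 21/(1 − d) − 21 | Analysed rate | Chance of success |
|---|---|---|---|---|
| 0 | 0 | 0 | 0.6000 | 9.05% |
| 1% | 2.5% | 0.21 | 0.6061 | 10.0% |
| 2% | 5% | 0.43 | 0.6122 | 11.0% |
| 5% | 12.5% | 1.11 | 0.6316 | 14.8% |

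**Step 4: effect on the reported rate.** A result of 16/21 = 76.2% would be 16/22 = 72.7% if one such patient had been dropped, and 16/23 = 69.6% if two had.

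**Step 5: a PR first seen at Cycle 6, taken separately.** A PR first seen at Cycle 2 or 4 can be confirmed by the Cycle 6 scan. One first seen at Cycle 6 has no scheduled scan until after Cycle 9, while surgery may come within one further cycle. That cycle is 28 days, longer than the 3-week interval, so a confirming scan before surgery is possible. If it confirms the PR, routes 2 and 3 are both met. Only without such a scan does the patient fall into the same gap.

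How an unconfirmed late PR is handled affects power. At a true rate of 85%, let u be the share of all patients with such a PR (assumed). Counted as non-responses, the rate is 0.85 − u; excluded and replaced, it is (0.85 − u)/(1 − u).

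| u (assumed) | Counted as non-response | Excluded and replaced |
|---|---|---|
| 0 | 90.4% | 90.4% |
| 5% | 75.0% | 88.5% |
| 10% | 54.7% | 86.1% |

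**The case against.** The strongest reply is that clause (2) is meant only for surgery that cuts the window short. Best response is judged over 6 cycles, planned surgery comes after them, and 10.3.4 says best response concerns larotrectinib and not resection. SD at two consecutive scans already fixes a best response of stable. For an SD patient there is no confirmation time at all, so the clause is arguably undefined rather than failed. Every provision keeps a function under this reading, and never-dosed patients would still use part of the 10% allowance. The reading is plausible, and may well be what was intended. But the clause contains no such limit. Reading the catch-all sentence as covering evaluable patients only would remove one conflict and still leave the SD patient excluded.

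A reader might also infer that every patient with a PR first seen at Cycle 6 is lost. The documents do not support that. Sections 4.3.2 and 7.1 direct sites to the confirmation rule in 10.4, and there is time for a second scan before surgery. What stays open is whether confirmation after Cycle 6 falls within the evaluation period and is centrally reviewed, since 7.4 routinely covers imaging only through Cycle 6.

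Nor does dropping a patient always inflate the ORR. That holds for non-responders; dropping a genuine late responder does not inflate the true response rate.

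Finally, accrual is complete (2.7.1), so replacement and the design's operating characteristics can no longer change. That limits the remedy to clarification and reporting, but the denominator still needs to be stated.

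**Conclusion.** The concern holds for patients with SD through the window who are then resected as planned. The literal text excludes and replaces them, other sentences in 9.4 make them non-responders, and the conflict is unresolved. The bias has one direction for this group: the ORR rises or is unchanged.

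The group is probably small. Section 2.3.2 reports response in all 7 earlier patients with infantile fibrosarcoma, and 2.4.1 reports response within 4 months in 12 of 15 children with TRK fusions and measurable disease. Under assumed shares of 1% to 5% of treated patients, the chance of success at a 60% all-treated ORR is 10.0% to 14.8%. These figures are a sensitivity range, not an estimate.

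A reader might infer that the stated type I error is wrong or that the trial's ORR was in fact inflated. Neither follows: 9.05% is right for evaluable patients, and the documents do not show that any patient was dropped on this ground. The point should be fixed; confidence is medium because the contrary reading is reasonable.

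**What to change.** - In 9.4, limit the surgical condition in clause (2) to resection before the 6-cycle evaluation period ends. Patients who complete the window with SD and are then resected count as evaluable non-responders; mid-window resections without a confirmed response stay non-evaluable.
- Beside the evaluable-patient ORR, report the ORR over all treated patients, with the number excluded and the reason for each, including mid-window resections.
- State in 9.4 whether confirmation after Cycle 6 counts and is centrally reviewed. List separately any PR first seen at Cycle 6 and not confirmed before surgery, and show the ORR both ways.
- Record this as a post-accrual clarification and, where results are already reported, apply it as a supplementary analysis.

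The cost is a short clarification of 9.4 and a supplementary table, with no new data collection. The ORR may come out slightly lower. If unconfirmed late PRs are counted as non-responses, the power cost is that in Step 5 (90.4% to 75.0% if they are 5% of patients, assumed), which is why both versions should be shown.

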7.4 Imaging Central Review

Central imaging review will be conducted for all imaging through Cycle 6. Additional central review of imaging evaluations performed for study participants during therapy or follow up on individual basis will occur as determined by the study committee and study radiologist. COG Operations Center will notify the Imaging Research Center of any patient requiring central review. The Imaging Research Center will then request that the treating institution forward the pertinent images for central review. The central image evaluation results will be entered into Rave for review for data analysis. Central imaging review will be performed retrospectively and will not be used to guide individual patient management.

The images are to be forwarded electronically to the Imaging Research Center at Children's Hospital Los Angeles via the ImageInBox.

COG institutions that are not connected via the ImageInBox can send the images on hard copy film, CD ROM, DVD, USB flash drive or by FTP. Submitted imaging studies should be clearly marked with the COG patient ID, study number (ADVL1823) and date, and shipped to [name] at the address below:

[name], CCRP
Administrator, Imaging Research Center
Children's Hospital Los Angeles
[name]
[name]
[contact]
[contact]
Email: [contact]

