9.2 Study Design

The primary endpoint will be objective response according to the disease specific criteria in [Section 10](#). The best response of disease to larotrectinib will be examined separately in the primary disease stratum and the secondary strata if sufficient enrollment occurs. The following Simon’s minimax two-stage design will be used in each stratum.

| | Cumulative Number of Responses | Decision |
|--|-----------------------------------|---|
| Stage 1: Enter 9 patients | 5 or fewer | Terminate the trial: agent ineffective |
| | 6 or more | Inconclusive result, continue trial (proceed to Stage 2) |
| Stage 2: Enter 12 additional patients | 15 or fewer | Terminate the trial: agent ineffective |
| | 16 or more | Terminate the trial: agent effective |

We will consider larotrectinib not of sufficient interest for further evaluation in a disease category if the true response rate is 60% and of sufficient activity if the true response rate is 85%. If larotrectinib has a true response rate of 60%, the rule described above will

identify it of sufficient activity for further study with probability 9.05% (type I error), and the trial will have an expected sample size of 14.8 with 51.74% probability of early termination. If larotrectinib has a true response rate of 85%, the rule described above will identify it of sufficient activity for further study with probability 90.40% (power against the alternative hypothesis $p = 0.85$).

If there are 9 confirmed objective responses before observing any nonresponders in Cohort A, consideration of closing Cohort A to enrollment will be discussed by all approved parties (i.e., DSMC, Bayer, and CTEP) following release of the response data by the DSMC. Nine responses among the first 9 response evaluable patients will exclude a true response rate of 60% with $p = 0.014$. If at any time there are 16 confirmed responses in a cohort, then enrollment to that cohort will be closed as the efficacy endpoint for that cohort has been met.

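### Sections 7.4 and 9.4 differ on whose scans are read centrally for the primary endpoint; under 9.4 the confirmed response rate can be biased downward

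*Combined protocol and SAP*

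**What the plan says.** Section 7.4 (Imaging Central Review) is unconditional: "Central imaging review will be conducted for all imaging through Cycle 6". It adds that the review is retrospective and does not guide patient care. It also describes a request process in which the operations center tells the imaging center which patients need review, and the site then sends the images.

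Section 9.4 (Evaluability for Response) fixes the endpoint. A CR or PR confirmed by central review is a response for the rule in 9.2, every other patient is a non-responder, and best response is judged over six cycles. On which scans are read, it says "All patients considered to have a response (CR or PR) must have imaging studies reviewed centrally at the COG", and then "Centers will be notified by the COG about requests for scans of patients with stable disease". It gives no criterion for making such a request and does not mention scans of patients called progressive locally. It cites 7.4 only for shipping.

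Section 9.2 (Study Design) sets the null rate at 60% and the alternative at 85%. It states a type I error of 9.05% and gives the power at the alternative in these words: "further study with probability 90.40% (power against the alternative hypothesis". It does not say whether 60% and 85% are institutional or centrally confirmed rates.

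**The concern.** The six-cycle window in 7.4 is the window for best response in 9.4, so both sections govern the same scans. They need not lead to the same reads.

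Under 7.4, a patient's chance of being read centrally does not depend on the local call. Under 9.4 taken alone, it does. Every local CR or PR goes to central readers and can be lost. A local stable disease that central readers would call PR is scored as a non-responder unless its scans are requested. Verification then depends on the outcome, and the errors it can correct lie mainly in one direction.

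Two things are at stake. The reported response rate could be too low. And because nothing says which stable-disease scans are requested, that choice could settle a close result: with 21 patients, one reclassified patient separates 15 responses (ineffective) from 16 (effective). The same holds at the Stage 1 boundary of 5 versus 6 responses in 9.

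**Working it through.** **Scope, side by side**

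| Local call through Cycle 6 | Section 7.4 | Section 9.4 |
|---|---|---|
| CR or PR | read centrally | read centrally (mandatory) |
| Stable disease | read centrally | on request, no criterion |
| Progression | read centrally if imaged | not mentioned |

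**Inputs (Section 9.2).** Stage 1: 9 patients, continue with 6 or more responses. Stage 2: 12 more patients, success with 16 or more responses in 21. Null rate 0.60, alternative 0.85.

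**Formula.** With p the true rate of the response that is counted,

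P(success) = Σ over x = 6 to 9 of P(X₁ = x) × P(X₂ ≥ 16 − x), where X₁ ~ Bin(9, p) and X₂ ~ Bin(12, p).

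**Stated figures reproduced**

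| x | P(X₁ = x), p = 0.85 | P(X₂ ≥ 16 − x) | Product |
|---|---|---|---|
| 6 | 0.1069 | 0.7358 | 0.0787 |
| 7 | 0.2597 | 0.9078 | 0.2357 |
| 8 | 0.3679 | 0.9761 | 0.3591 |
| 9 | 0.2316 | 0.9954 | 0.2305 |

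The sum is 0.9040, the stated power. At p = 0.60 the same sum is 0.0905, the probability of early termination is 0.5174, and the expected sample size is 9 + 12 × (1 − 0.5174) = 14.8. All agree with 9.2.

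**Hypothetical sensitivity.** Suppose 60% and 85% are the rates that would be seen with every scan read centrally, and that following 9.4 misses a share m of those responders because they were called stable locally and never requested. The counted rate is then p(1 − m). The documents give no value for m; 2%, 5% and 10% are assumptions.

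| m | 0.85(1 − m) | Power | 0.60(1 − m) | Type I error |
|---|---|---|---|---|
| 0 | 0.850 | 90.4% | 0.600 | 9.05% |
| 2% | 0.833 | 86.0% | 0.588 | 7.4% |
| 5% | 0.8075 | 77.7% | 0.570 | 5.4% |
| 10% | 0.765 | 61.0% | 0.540 | 3.0% |

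In counts: at 85%, 21 × 0.85 = 17.85 responses are expected, and 5% of these is 0.05 × 17.85 = 0.89. The drop from 90.4% to 77.7% therefore corresponds to about one missed responder in a full cohort.

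**The case against.** **The sections can be read together.** 9.4 makes review mandatory for responders but never says that only they are reviewed. On this reading 7.4 sets the scope, 9.4 sets a floor, and the stable-disease sentence is logistics, since 7.4 also works by request. This is possible. But if every scan through Cycle 6 is read anyway, a separate mandate for responders and a separate request path for stable disease have no clear function. Nothing says which section governs.

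**A reader might infer that the stated power is wrong.** The documents do not support that. The figure is exact for the rule at 85%, and 9.4 defines the counted response as centrally confirmed, so 85% can be that rate. Incomplete reading would move the trial along the power curve; it does not make the curve wrong.

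**The miss rates have no source.** This stands. The one comparison in the documents (Section 2.3.2: 75% by independent review, 80% by investigators, 55 patients) is a net local over-call in a mixed adult and pediatric population. It does not measure local under-calling. Imaging after Cycles 2, 4 and 6 also gives a local response several chances to be called and so trigger review.

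**The bias is conservative and accrual is over.** Both stand. Type I error falls, so an activity claim is not inflated. Section 2.7.1 reports completed accrual and high activity, so an edit now serves the definition and reporting of the endpoint. It cannot restore power.

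**Conclusion.** The mismatch between 7.4 and 9.4 is real, needs no assumed rate to show, and concerns the definition of the primary endpoint. It should be reconciled. If 9.4 is followed as worded, the centrally confirmed response rate may be biased downward, and an undefined request for a stable-disease scan could change the decision at 15/16.

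The size is unknown. The power range of 86.0% to 61.0% rests on two assumptions: that 85% means the rate with every scan read, and that 2% to 10% of those responders are missed. If 85% is already the rate of the counted response, power is 90.40% as stated. The sensitivity shows how few missed responders would matter in a cohort of 21. It is not an estimate of what happened. If 7.4 was followed in practice, there is no bias and only the wording needs repair.

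**What to change.** In Section 9.4, replace the sentence on responders and the one on requests for stable-disease scans with:

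> All disease imaging through Cycle 6 of every solid-tumor patient in the response analysis, whatever the institutional assessment, is reviewed centrally per Section 7.4, and the central read determines the response counted in Section 9.2. Patients with progression declared without imaging are counted as non-responders, unless a response had already been centrally confirmed. Cohort C is assessed by Sections 10.6 and 10.7.

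The second sentence is needed because Sections 4.3.2 and 7.1 let investigators declare progression without radiographic confirmation; its exception follows Table 1 in Section 10.4, where a confirmed response before progression stands. The third is needed because leukemia response rests largely on marrow and blood counts.

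In Section 9.2, state that 60% and 85% are centrally confirmed rates.

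The cost is small: short edits to two sections. Section 7.4 already plans these reads, so no new scans or readers are required. Any extra work is image transfer for patients with local stable disease or progression whose scans have not yet been sent.
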